### **5.2.2 Prohibited Treatment**

As per the exclusion criterion in Section 4.2, the only allowable concurrent 2nd line IV AED therapies to treat the current episode of SE are fosphenytoin/phenytoin, valproic acid, levetiracetam, lacosamide, or brivaracetam. Administering fosphenytoin and/or phenytoin will be counted as one (1) AED. These drugs can be used alone or in combination with each other. If the subject is receiving oral AED therapy to manage a subject's chronic medical condition, for example, epilepsy, migraine, or neuropathic pain, that therapy is acceptable and should continue unchanged, if feasible and medically justified. This prophylactic treatment does not count towards the SE treatment failures required to qualify for this study. If any of these oral AED medications had to be interrupted around the time of the current SE episode, it is recommended that they would be re-started 10 hours after study drug initiation, if medically acceptable. Also, subjects who have been enrolled in another clinical study for SE are required to have a reasonable expectation that the other investigational drug has been cleared from their system, that is, that five half-lives have elapsed. Subjects on IV AEDs that are standard of care can be enrolled in the study. Subjects who have taken exogenous allopregnanolone or ganaxolone previously are not eligible for the study.

If a subject progresses at any time during the study to an IV anesthetic drug (a 3rd line treatment; e.g. midazolam, propofol, thiopental, pentobarbital, or ketamine and/or 4th line treatment; e.g., immunosuppressants, magnesium) for seizure suppression, study drug administration will be discontinued, however the subject will continue with the in-patient follow-up day and the week 2, 3, and 4 follow-up visits.

## 6. STUDY DRUG

### 6.1 Identity of Study drug

The test product is ganaxolone IV solution, which will be provided in glass vials/bottles.

For the Open-Label Group, ganaxolone IV solution, 1 mg/mL – 100 mL/vial is a sterile solution containing 1 mg of the active ingredient ganaxolone per 1 mL solution. Ganaxolone IV Solution, 1 mg/mL – 100 mL/vial is packaged as a 100 mL dose in 125 mL glass vials. Details of packaging, dose and administration of the ganaxolone IV solution and placebo for the double-blind group will be included in a future amendment.

The formulation consists of a sterile solution of ganaxolone drug substance that has been solubilized by complexation with Captisol® (Betadex Sulfoxbutyl Ether Sodium). In addition to Captisol, the formulation consists of water for injection (diluent), buffering agents (potassium phosphate, sodium phosphate) and sodium chloride (tonicity modifier). The drug product is terminally heat sterilized.

The composition of the Ganaxolone IV Solution, 1 mg/mL – 100 mL/vial is provided below.

### Quantitative Composition of Ganaxolone IV Solution, 1 mg/mL – 100 mL/Vial

Component	Reference to Standards	Content per mL (mg/mL)	Concentration (%w/w)	Function
Ganaxolone	Marinus	1.00	0.097	Active ingredient
Betadex sulfobutyl ether sodium (Captisol)	NF	59.74	5.817	Solubilizing agent
Potassium phosphate, monobasic (KH 2 PO 4 )	NF	2.46	0.239	Buffer agent a
Sodium phosphate, dibasic heptahydrate (Na 2 HPO 4 .7H 2 O)	USP	2.78	0.271	Buffer agent a
Sodium chloride	USP	2.00	0.195	Tonicity modifying agent
Water for injection	USP	q.s. 1 mL	93.381	Diluent

NF = National Formulary; USP = United States Pharmacopeia; w/w = weight by weight.

a Formulation pH = 6.4

**Drug Product Name:** Ganaxolone IV Solution, 1 mg/mL – 100 mL/vial

**Manufacturer:** Alliance Contract Pharma, LLC., Harleysville, PA 19438 USA

**Strength for Open-Label Group:** ready-to-infuse 1-mg/mL sterile solution in a glass vial

**Packaging:** Ganaxolone IV Solution, 1 mg/mL – 100 mL/vial will be provided to the site as individual vials containing 1 mg/mL of Ganaxolone.

Changes to sponsor-supplied packaging prior to dosing may not occur without full agreement in advance by the sponsor.

**Storage:** The investigator has the overall responsibility for ensuring that study drug is stored in a secure, limited-access location. Limited responsibility may be delegated to the pharmacy or member of the study team, but this delegation must be documented. Study drugs are distributed by the pharmacy or by a nominated member of the study team.

Ganaxolone IV solution, 1 mg/mL – 100 mL/vial has on-going stability and to date has been found stable if stored at 15°-25°C (59°-77°F) until use. Excursions up to 30°C (86°C) that are experienced in pharmacies, hospitals, and warehouses, and during shipping are allowed.

### **6.1.1 Blinding the Treatment Assignment**

For the double-blind group, the site pharmacy personnel who dispenses the study drug is not required to be blinded and will not be involved in any study assessments. All other participating staff involved in the evaluation and execution of the study will remain blinded to subject's study drug treatment.

## **6.2 Administration of Study drug(s)**

### **6.2.1 Interactive Response Technology for Study Drug Management**

For the double-blind group an Interactive Voice/Web Response System (IVRS/IWRS) will be utilized for the following study drug tasks:

- Randomization
- Supply management
- Inventory management and supply ordering
- Expiration date tracking
- Returns
- Emergency unblinding

Details on the name and address of the system and use will be detailed in the Investigator files at each site.

### **6.2.2 Allocation of Subjects to Treatment**

This is a double-blind study with an initial open-label group. The actual treatment given to individual subjects in the double-blind group is determined by a randomization schedule. For both groups, subject identification numbers are assigned to all subjects prior to dosing. Within each site (numbered uniquely within a protocol), subject numbers are assigned per the sequence of subject presentation for study participation.

The randomization number represents a unique number corresponding to study drug allocated to the subject, once eligibility has been determined.

Individual subject treatment for the double-blind is automatically assigned by the IVRS/IWRS.

Subjects participating in the open-label portion of the study will be dispensed ganaxolone IV solution. The study drug will be identified as ganaxolone IV solution and any vial identified as such can be dispensed. Sites will be responsible for logging and tracking the open-label supplies via study accountability logs and entered into the eCRF. All open-label supplies will have a unique vial number for tracking purposes.

### **6.2.3 Dosing**

Total adjunctive ganaxolone IV solution therapy infusion treatment is planned to be 2 days which includes a 12-hour study drug taper. All subjects will have an ~3-minute bolus dose with a continuous infusion at the rate of 20-80 mg/hour, and a 12-hour study drug taper (see Table 2 and 3 for details). Once study drug administration is started it should be delivered for 2 days (48 hours) which includes a 12-hour taper.

Study drug should be administered, ideally, through a dedicated (peripheral or central) IV line. These infusion parameters result in daily doses of ganaxolone of  $\leq$  830 mg/day and Captisol of  $\leq$  50 g/day as agreed upon with the FDA. Based on PK modeling, it is predicted that maximum concentrations of ganaxolone should remain within 1,000 ng/mL during infusion, but some variability is expected due to, for example, differences in subjects' weight. Note, at any time, the infusion rate of the ongoing administration may be decreased for safety reasons, see Dose Adjustments and Interruptions section below for more information.

Note, pharmacokinetic data from study 1042-0405 in healthy volunteers showed that a bolus infusion of 30 mg ganaxolone over 5 minutes led to transient peak concentration levels ( $C_{max}$ ) above 1,000 ng/mL (maximal observed  $C_{max}$  was 1,850 ng/mL) with no safety concerns. Infusion of 30 mg/hour for 1 hour and 20 mg/hour for 4 hours led to concentrations of 258 and 215 ng/mL, respectively, again without any safety concerns (see Section 1.2 Product Background and Clinical Information).

During the open-label group, based on the safety, efficacy, and pharmacokinetic data from the ongoing study, the infusion parameters in subsequent subjects may be adjusted to maximize the safety and efficacy of study subjects. If the infusion parameters are amended, the new infusion parameters will not exceed the daily limit of 50 g/day Captisol ( $\leq$  830 mg/day ganaxolone) as agreed upon with the FDA. The revised infusion parameters will be communicated to Clinical Sites in a Protocol Administrative Change Memo and kept in the study and site files.

Potential subjects must have failed one 2nd line IV AED therapy, administered at an appropriate dose and duration to show efficacy. Ganaxolone IV solution (open-label group) or ganaxolone IV solution or placebo (double-blind group) will be administered in combination with standard of care at the time that the first 2nd line IV AED has failed and the second 2nd line AED is medically indicated during the treatment of SE. Study drug must be administered with 2nd line IV AED treatment and should be initiated as close to the dose initiation of the second 2nd line IV AED as possible.

Upon administration of study drug, subjects will be monitored for improvement or resolution of SE (clinical or EEG response).

Note, the infusion rate cannot be rounded-up regardless whether dosing is in subjects  $\geq 40$  kg or  $< 40$  kg.

Subjects weighing at least 40 kg:

- A 30-mg bolus dose (over ~3 minutes) will be administered with a continuous infusion of 80 mg/hour for 2 hours followed by a continuous infusion rate of 40 mg/hour for 10 hours, and then 20 mg/hour for the remaining 12 hours of Day 1.
- On Day 2 (24-36 hours) the continuous infusion rate of 20 mg/hour will continue until the start of the study drug taper at 36 hours post study drug initiation. If needed, to manage seizure relapse or another medical reason, the infusion rate can be increased from 20 mg/hour up to a maximum rate of 45 mg/hour at any time during hours 24-36 of Day 2.
- To taper the study drug, the infusion rate at the 36-hour post study drug initiation timepoint will be reduced by 33.3% every 4 hours until the infusion is stopped or if the infusion rate becomes too low to sustain the infusion line, at which point it will be stopped. The first taper will be 33.3% from the current infusion rate, the second taper will be 33.3% from the first tapered infusion rate, and the final taper will be 33.3% from the previous tapered infusion rate. If, per the investigator's judgment, the study drug taper needs to start at an earlier timepoint during the treatment period, the infusion rate at the start of the first taper will be decreased by 33.3% every 4 hours as described.
- At the time the study drug infusion is discontinued the subject will progress to the in-patient follow-up day assessments/procedures.

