**Table 2: Dosing for Subjects  $\geq 40$  kg (on an mg/hour basis)**

Days	Start Time from Study Drug Initiation	Study Drug Dose (mg/hour)	Study Drug Infusion Rate (mL/hour)	Duration
Day 1	0 hours: bolus dose via syringe or infusion pump	30	30	3 minutes
Day 1	0 hours through 2 hours post study drug initiation: continuous infusion, started with bolus	80	80	2 hours
Day 1	2 hours through 12 hours post study drug initiation	40	40	10 hours
Day 1	12 hours through 24 hours post study drug initiation	20	20	12 hours
Day 2 a	24 hours through 36 hours post study drug initiation	20 - 45	20 - 45	12 hours
Study Drug Taper				
Day 2 b	36 through 48 hours post study drug initiation (12-hour taper)	13.34 - 30.02	13.34 - 30.02	4 hours
		8.90 - 20.02	8.90 - 20.02	4 hours
		5.93 - 13.35	5.93 - 13.35	4 hours

a. On Day 2 (24-36 hours), the continuous infusion rate can be increased from 20 mg/hour to a maximum rate of 45 mg/hour at any time, if needed, to manage seizure relapse or other medical reason.

b. To taper the study drug, the infusion rate at the 36-hour post study drug initiation timepoint will be reduced by 33.3% every 4 hours until the infusion rate is stopped or if the infusion rate becomes too low to sustain the infusion line, at which point it will be stopped. The first taper will be 33.3% from the current infusion rate, the second taper will be 33.3% from the first tapered infusion rate, and the final taper will be 33.3% from the previous tapered infusion rate. If, per the investigator's judgment, the study drug taper needs to start at an earlier timepoint during the treatment period, the infusion rate at the start of the first taper will be decreased by 33.3% every 4 hours as described.

Subjects weighing  $< 40$  kg will be dosed on a per-kilogram basis:

- A 0.43-mg/kg bolus dose (over ~3 minutes) will be administered with a continuous infusion at a dose of 1.14 mg/kg/hour for 2 hours followed by a continuous infusion rate of 0.57 mg/kg/hour for 10 hours, and 0.29 mg/kg/hour for the remaining 12 hours of Day 1.
- On Day 2 (24-36 hours) the continuous infusion dose of 0.29 mg/kg/hour will continue until the start of the study drug taper at 36 hours post study drug initiation. If needed, to manage seizure relapse or for another medical reason, the infusion dose can be increased from 0.29 mg/kg/hour up to a maximum of 0.64 mg/kg/hour at any time during hours 24-36 of Day 2.

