- To taper the study drug, the infusion rate at the 36-hour post study drug initiation timepoint will be reduced by 33.3% every 4 hours until the infusion is stopped or if the infusion rate becomes too low to sustain the infusion line, at which point it will be stopped. The first taper

will be 33.3% from the current infusion rate, the second taper will be 33.3% from the first tapered infusion rate, and the final taper will be 33.3% from the previous tapered infusion rate. If, per the investigator's judgment, the study drug taper needs to start at an earlier timepoint during the treatment period, the infusion rate at the start of the first taper will be decreased by 33.3% every 4 hours as described.

- At the time the study drug infusion is discontinued the subject will progress to the in-patient follow-up day assessments/procedures.

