### Dose Adjustments and Interruptions:

Dose (infusion rate) decreases and interruptions of the continuous infusion are discouraged at any time during study drug treatment. However, if there is an urgent medical need (e.g., severe hypotension, acidosis, severe sedation) or a subject’s standard of care requires they undergo a

procedure for which the infusion would need to be decreased or interrupted (e.g., an MRI scan) it should be kept as short as possible but no longer than 6 hours. If > 6 hours the Marinus Medical Monitor must approve the re-start of the infusion.

Note:

- After the dose (infusion rate) decrease or infusion interruption, it will be per the investigator's judgment and assessment of risk/benefit if the subject should continue in the study or early discontinue.
- In cases when severe sedation is seen and early drug discontinuation is being considered, the Marinus Medical Monitor should be contacted prior to infusion termination, if feasible.
- If the decision is made for the subject to continue in the study, the infusion should be restarted at the rate matching the rate at the corresponding nominal time, counted from the beginning of the study drug infusion on Day 1. A study drug bolus or "catch-up" dose to deliver the study drug that was missed during the interruption should not be administered.
- Dose (infusion rate) increases above those specified in the protocol (or based on a future Protocol Administrative Change Memo) are not allowed at any time during infusion. This is to ensure daily Captisol and ganaxolone limits are kept  $\leq$  50 g/day and  $\leq$  830 mg/day, respectively.

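### The early-taper rule ignores the scheduled step-down at hour 12, so a taper begun between hours 8 and 12 runs for up to just under 4 hours above the rate of a subject who does not taper (minor)

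*Protocol*

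**What the plan says.** For subjects of at least 40 kg, Protocol section 6.2.3 sets the Day 1 infusion in three stages. It opens with this: "A 30-mg bolus dose (over ~3 minutes) will be administered with a continuous infusion of 80 mg/hour for 2 hours". The rest of Day 1 is "followed by a continuous infusion rate of 40 mg/hour for 10 hours, and then 20 mg/hour for the remaining 12 hours of Day 1". Table 2 repeats the lower rate in its row for "12 hours through 24 hours post study drug initiation". Below 40 kg the corresponding stages, in the text after Table 2 and in Table 3, are "0.57 mg/kg/hour for 10 hours, and 0.29 mg/kg/hour for the remaining 12 hours of Day 1".

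The standard taper starts at hour 36 and compounds: "The first taper will be 33.3% from the current infusion rate, the second taper will be 33.3% from the first tapered infusion rate". Section 6.2.3 then adds a rule for an earlier start. It opens "If, per the investigator's judgment, the study drug taper needs to start at an earlier timepoint during the treatment period" and continues "the infusion rate at the start of the first taper will be decreased by 33.3% every 4 hours as described". The synopsis, the footnotes to Tables 2 and 3, and the text for subjects below 40 kg carry the same rule. Tables 2 and 3 print taper rates only for the hour-36 start.

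Two neighbouring provisions matter. Under Dose Adjustments and Interruptions, infusion rate "increases above those specified in the protocol (or based on a future Protocol Administrative Change Memo) are not allowed at any time". The same section matches the rate to nominal time, but only when the infusion is restarted after a decrease or interruption.

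**The concern.** At hour 36 the taper starts from a rate that has no further step-down scheduled, so any 33.3% cut lowers the rate below what would otherwise have run. On Day 1 that is not so, because the schedule itself halves the rate at hour 12. A 33.3% cut is smaller than a halving. A 4-hour step begun from the higher rate shortly before hour 12 therefore carries over into a period in which an untapered subject would be on less.

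The window is reachable. The synopsis and Table 1 footnote i allow pregnancy and drug-screen samples to be taken after the infusion has started. If the investigator then discontinues study drug, they refer the site to the taper directions. That is a documented route to a taper on Day 1.

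What is at stake is limited but real: a rule meant to withdraw the drug can, if followed exactly, give a higher rate for a few hours than continuing would. No section says what happens to a taper step that crosses hour 12.

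**Working it through.** **Inputs** (Protocol 6.2.3, Tables 2 and 3). Retained fraction per step: 1 − 0.333 = 0.667. Steps: three of 4 h. Scheduled rates: 40 then 20 mg/h, or 0.57 then 0.29 mg/kg/h, changing at hour 12. Bolus 30 mg, then 80 mg/h for 2 h. Start of taper: hour t.

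**Reproducing the plan's own figures.** From 20 mg/h: 20 × 0.667 = 13.34, × 0.667 = 8.90, × 0.667 = 5.93. From 45 mg/h: 30.02, 20.02, 13.35. These match Table 2. Day 1 without a taper: 30 + 2 × 80 + 10 × 40 + 12 × 20 = 830 mg, matching the stated limit. The rule is therefore being read as the protocol applies it.

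**Early taper from 40 mg/h.** Steps: 26.68, 17.80 and 11.87 mg/h. Total: 4 × (26.68 + 17.80 + 11.87) = 225.4 mg.

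**Rate.** The first step ends at t + 4, which is after hour 12 only if t > 8. For 8 < t < 12 the rate from hour 12 is 26.68 against 20 mg/h (26.68/20 = 1.33) for t − 8 hours. Later steps are below 20. A start at hour 12, once the rate is 20, would have a first step of 13.34 mg/h; a start just before has 26.68. Below 40 kg: 0.57 × 0.667 = 0.38 against 0.29 mg/kg/h (ratio 1.31).

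**Dose in the first 4 h.** Taper: 4 × 26.68 = 106.7 mg. Schedule: 40(12 − t) + 20(t − 8) = 320 − 20t mg. The taper gives more only if t > (320 − 106.72)/20 = 10.66 h.

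**Dose over the full 12-h taper.** Schedule: 40(12 − t) + 20t = 480 − 20t mg, which exceeds 240 mg for every t < 12. The taper gives 225.4 mg, so it always gives less.

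| Start (h) | Hours above schedule | First 4 h: taper vs schedule (mg) | Ahead on cumulative dose until (h after start) | Full 12 h: taper vs schedule (mg) |
|---|---|---|---|---|
| 9 | 1 | 106.7 vs 140 | never ahead | 225.4 vs 300 |
| 10 | 2 | 106.7 vs 120 | never ahead | 225.4 vs 280 |
| 11 | 3 | 106.7 vs 100 | about 7 | 225.4 vs 260 |
| 11.5 | 3.5 | 106.7 vs 90 | about 9 | 225.4 vs 250 |
| just before 12 | almost 4 | 106.7 vs 80 | about 10 | 225.4 vs 240 |

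The last row is the limiting case. The excess peaks at 26.7 mg after 4 h and falls to 177.9 − 160 = 17.9 mg after 8 h. It then shrinks by 20 − 11.87 = 8.13 mg each hour, reaching zero at 8 + 17.9/8.13 = 10.2 h.

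**Daily limit.** Largest Day 1 total with such a taper: 30 + 160 + 400 + 225.4 = 815.4 mg, below 830 mg.

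**Below 40 kg, dose.** First 4 h: 4 × 0.38 = 1.52 mg/kg against 0.57(12 − t) + 0.29(t − 8) = 4.52 − 0.28t, so more only if t > 10.71 h (at most 1.52 against 1.16 mg/kg). Full taper: 3.21 mg/kg against more than 3.48 mg/kg.

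**The case against.** The strongest reply is that the hour 12–24 row describes continuing treatment. Once a taper begins, the early-taper sentence replaces the schedule and states its own base. On that reading nothing is contradicted; the comparison is with a schedule the subject has left. Rates above 20 mg/h are also not foreign to a taper, since Table 2 prints a first step of up to 30.02 mg/h. Much of this stands. No printed figure is wrong, and the text can be read coherently. It does not remove the result that a subject being withdrawn runs above one who continues, which the text neither acknowledges nor resolves.

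Four stronger readings are tempting, and the documents do not support them.

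- A reader might infer a breach of the bar on rate increases. During an early taper the rate only falls (40, 26.68, 17.80, 11.87), by a rule the protocol itself specifies. The bar's stated purpose is the daily limit, which holds.
- A reader might infer that an early taper gives more drug overall. The full taper always gives less.
- A reader might infer that exposure or safety data will be misread as reduced dosing. The SAP groups subjects by target dose, not by early taper, and section 4.9.7 lists all doses administered.
- A reader might infer that sites have nothing to check against. Tables 2 and 3 lack early-taper rates, but the protocol sends sites to the Pharmacy Manual, which is not available here.

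The safety implication is also limited. Section 6.2.3 separately allows the rate to be decreased for safety, and the drug to be stopped without a taper when continuing is no longer safe. The rule does not hold an unsafe subject on the first taper step.

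**Conclusion.** The point holds as a minor inconsistency. For every start strictly between hours 8 and 12, in both weight groups, the rule as written gives a rate about 33% (31% below 40 kg) above the untapered schedule from hour 12, for just under 4 hours at most. A cumulative excess needs a start after about hour 10.7, never exceeds about 27 mg at 40 kg or more, and is temporary.

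This rests on the plain reading that the cut applies to the rate running when the taper starts and is held for 4 hours. The rate finding does not depend on whether later cuts compound, because the first step is the same either way. The dose comparisons use the compounding that reproduces Table 2, and take the untapered subject as staying on the scheduled rates. How often tapers will start in this window cannot be judged from the documents.

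**What to change.** Reconcile the early-taper sentence with the hour-12 step-down in Tables 2 and 3, and state which governs when the two give different rates for the same hour. Make the same change wherever the sentence is repeated: the synopsis, both weight-group texts in section 6.2.3, and the footnotes to Tables 2 and 3. Carry it into the Pharmacy Manual. The choice of rule is for the sponsor and its clinicians, and no rate is proposed here. The cost is one sentence, repeated, and a matching manual update. Sample size and analyses are unaffected.
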